## **6 Research methods**

### **6.1 Study design**

This study will be a site-based retrospective non-interventional medical chart review of pediatric and adult male and female patients with PROS. This study will abstract longitudinal information that has been previously recorded in the medical charts of patients with PROS to assess the efficacy and safety of alpelisib for the treatment of the heterogeneous manifestations of PROS.

Patient-level data will be abstracted from medical charts of all eligible patients at all participating sites and will be pooled and assessed. Trained personnel at each site will abstract medical chart data (see [Section 6.4](#) for additional information). Informed consent will be obtained prior to data abstraction, as appropriate, for eligible patients interested in participating in the study.

[figure not shown]
Patients with PROS who have received at least one dose of alpelisib initiated at least 24 weeks before the cut-off date will be included. The index (baseline) date will be defined as the date of alpelisib initiation. The pre-index date period will be defined as the period from up to 24 weeks prior to the index date through one day prior to the index date. The study period will be defined as the period from the index date up to the cut-off date ([Figure 6-1](#)).

The cut-off date (09-Mar-2020) is selected to minimize the impact of the COVID-19 pandemic on the data integrity. Eligible patients who initiated alpelisib on or before 23-Sep-2019 will have relevant assessments expected to occur on or before 09-Mar-2020. At that time of the cut-off, COVID-19 pandemic did not have major consequences on the regular management of the patients in the countries participating in the MAP.

Available information from all clinic visits during the pre-index date period will be abstracted; additionally, available prior PROS medications and PROS related surgical/vascular interventions will be collected since diagnosis.

During the study period, all available data will be collected from index date up to the cut-off date. If a patient has discontinued treatment prior to that date, only data reported up to 30 days after the last date of study treatment will be abstracted and entered into the database.

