3.5.1 Definition of response

Patients included in the analysis population for the primary endpoint will be defined as responders if they meet the following criterion:

- Patient achieved $\geq 20\%$ reduction from index date (or up to 24 weeks prior) in the sum of target lesion volumes (1 to 3 lesions, via central radiological assessment) by the change between the index date and 24 weeks or 6 months (+/- 4 weeks) following the index date
- None of the individual target lesions has $\geq 20\%$ increase from index date to Week 24 or 6 months (+/- 4 weeks)
- Patient did not permanently discontinue alpelisib prior to 24 weeks of treatment

- Patient did not require surgery as rescue therapy between index date and 24 weeks of treatment with alpelisib due to disease deterioration
- No progression of non-target lesions at Week 24 or 6 months (+/- 4 weeks)
- No appearance of new lesions at Week 24 or 6 months (+/- 4 weeks)

Patients will be defined as non-responders if they meet at least one of the following criteria:

- Patient achieved < 20% reduction from index date (or up to 24 weeks prior) in the sum of target lesion volumes (1 to 3 lesions, via central radiological assessment) by the change between the index date and 24 weeks or 6 months (+/- 4 weeks) following the index date
- Any of the individual target lesions has $\geq 20\%$ increase from index date to Week 24 or 6 months (+/- 4 weeks)
- Patient permanently discontinued alpelisib prior to 24 weeks of treatment
- Patient require surgery as rescue therapy between index date and 24 weeks of treatment with alpelisib due to disease deterioration.
- Progression of non-target lesions at week 24 or 6 months (+/- 4 weeks)
- Appearance of new lesion at week 24 or 6 months (+/- 4 weeks)
- Patients with MRI scan performed at week 24 or 6 months (+/- 4 weeks) for which the volumetric measurement of the selected target lesions (1 to 3 lesions, via central radiological assessment) cannot be calculated.

Patients will be considered as having a missing response if lesion volume(s) assessment at 24 weeks or 6 months (+/- 4 weeks) following the index date is not available and:

- Patient did not permanently discontinue alpelisib prior to 24 weeks of treatment and
- Patient did not require surgery as rescue therapy between index date and 24 weeks of treatment with alpelisib due to disease deterioration.

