All patients in the efficacy population without a missing response will be used for the primary analysis of the primary endpoint (complete case analysis).

Surgery as rescue therapy is considered as required due to worsening of any existing lesions or development of a new lesions requiring intervention while on alpelisib treatment.

Disease progression at any assessment is defined as an increase of any individual target lesions of $\geq 20\%$ in volume from previous assessment, progression of non-target PROS lesions or appearance of a new PROS lesion.

Progression based on non-target and new lesions will be based on radiological assessment of the central reader.

In relation to non-target lesions, progression will be assessed for the lesions that are identified at index date (or up to 24 weeks prior) with available information at Week 24 or 6 months (+/- 4 weeks) and new lesions. At Week 24 the central imaging reviewer will make a conclusion if overall level of non-target disease burden decreased or increased unequivocally.

Evaluation of radiographic response and progression of all measurable lesions (target and non-target) will be provide to Novartis by a third party vendor. All details are summarized in the Independent Central Review Charter (ICRC).

Table 3-3 Primary endpoint measure

Measure	Type of variable	Statistics	Time point for reporting
Proportion of patients with response at Week 24 provided that none of the individual target lesions have $\geq 20\%$ increase from index date and in absence of progression of non-target lesions and without new lesions	Binary	n, missing, frequency, percentage, 95% CI	At 24 weeks (6 months)

The primary analysis for this study will be descriptive in nature (estimation based), and therefore no hypothesis testing will be conducted. Categorical and binary data will be presented by frequency counts and percentages. The Clopper-Pearson exact method will be used to estimate 95% CIs for binary data.

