The change and percent change in lesion volume will be assessed as a continuous measure over time. A graphical representation, such as box plots at each time-point, will be provided to illustrate changes over time. A by patient graph will also be considered to depict individual trend. Additional information on time windows for each study key-time point following the index date are reported in Section 3.3.

Endpoints related to secondary objective #4: Duration of response (DOR)

Duration of response (DOR) is defined as the time from first documented response, to the date of the first documented disease progression or death due to any cause. This analysis only applies to responders (definition Section 3.5). The start date is the date of first documented

response, and the end date is defined as the date of the first documented disease progression or death due any cause. Patients continuing without event will be censored at the date of their last adequate lesion assessment (i.e. MRI scans performed to assess volumetric measurements).

DOR will be listed and summarized for all patients in the efficacy set with response. The distribution of duration of response will be estimated using the Kaplan-Meier method and the median will be presented along with 95% confidence interval only if a sufficient number of responses is observed.

Endpoints related to secondary objective #5: Description in type of medication and non-drug therapies (e.g., concomitant PROS-related medications, PROS-related surgeries and duration of treatment) over time.

This endpoint will assess the alpelisib exposure pattern in the study population, including any treatment interruption, dose changes and duration of treatment overall during the study period. The number of patients who have at least one dose adjustment, interruption, or discontinuation, and their reasons will be reported where available.

Furthermore, the concomitant utilization of PROS-related medications, such as those prophylactic antibiotics, pain medications and anti-epileptics, as well as PROS-related non-drug treatments, such as ketogenic diets and surgical corsets, will allow to establish an association between the efficacy of alpelisib (as measured by the primary end point) and symptomatic/clinical benefit for the patient.

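### The duration-of-response rules do not cover rescue surgery or stopping alpelisib for worsening, so duration can be overstated when no scan documents the progression

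*SAP*

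**What the plan says.** **End of response.** Under objective #4, SAP 3.6 states that "the end date is defined as the date of the first documented disease progression or death due any cause". Protocol 6.8.2 has the same end point.

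**Progression.** SAP 3.5.1 defines it through lesions: "Disease progression at any assessment is defined as an increase of any individual target lesions of" at least 20% in volume since the previous assessment, or progression of non-target lesions, or a new lesion. It adds: "Progression based on non-target and new lesions will be based on radiological assessment of the central reader".

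**Censoring.** SAP 3.6 gives one rule: "Patients continuing without event will be censored at the date of their last adequate lesion assessment". It does not mention a responder who has surgery or stops treatment.

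**Rescue surgery and stopping in the response definition.** SAP 3.5.1 lists both as grounds for non-response: "Patient require surgery as rescue therapy between index date and 24 weeks of treatment with alpelisib due to disease deterioration" and "Patient permanently discontinued alpelisib prior to 24 weeks of treatment". The same section explains what rescue surgery means: "Surgery as rescue therapy is considered as required due to worsening of any existing lesions or development of a new lesions requiring intervention" during alpelisib treatment.

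**Follow-up after stopping.** For a patient who discontinues before the cut-off, Protocol 6.1 says that "only data reported up to 30 days after the last date of study treatment will be abstracted". SAP 1.3 repeats this.

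**Sensitivity analyses.** Those in SAP 3.5.3 concern the primary endpoint. None is described for DOR.

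**The concern.** Up to 24 weeks of treatment, the SAP treats surgery for a worsening or new lesion as failure. After a Week 24 response, the same surgery has no effect on DOR unless imaging also meets the progression definition. The same holds for a responder who stops alpelisib because the disease is worsening.

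Kaplan-Meier estimation assumes that a censored patient has the same outlook as those still at risk. A patient censored around surgery for worsening, or around stopping for worsening, plainly does not. Removing such patients from the risk set without counting an event pushes the DOR curve upward.

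The amendment rationale in the protocol calls DOR important for assessing benefit, and Protocol 9 says the results are meant as primary data for health authorities. With few responders, two or three patients handled one way or the other can visibly change the curve.

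**Working it through.** The documents state no expected median DOR, event count or precision, so there is no figure to reproduce. The check has two parts.

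**1. The rules side by side**

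| Situation | Response at Week 24 (SAP 3.5.1) | DOR (SAP 3.6) |
|---|---|---|
| Scan shows progression | Non-responder if at Week 24 | Event |
| Death | Not listed | Event |
| Rescue surgery, no scan showing progression | Non-responder if before 24 weeks | Not an event; censoring not specified |
| Permanent discontinuation, no scan showing progression | Non-responder if before 24 weeks, whatever the reason | Not an event; censoring not specified |

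The last two rows matter only if worsening can occur without a qualifying scan. Protocol 6.9 says that clinical practice has no shared assessment schedule. SAP 3.5.3 says that imaging frequency varies with patient need, institution and insurance. After discontinuation the window for a further scan is 30 days. A missing scan is therefore possible, though nothing shows how often it occurs. If the censoring rule is stretched to these patients, they are censored at their last adequate MRI.

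The analysis set also differs. SAP 3.6 limits DOR to responders as defined in Section 3.5, so for them the gap concerns events after 24 weeks. Protocol 6.8.2 includes a response at any time. Under that wording, a patient with an early response and rescue surgery before Week 24 could be a primary non-responder with a DOR still running.

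**2. Possible size (all inputs assumed)**

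Let *h* be the constant hazard of any response-ending event. Let *f* be the share of those events that are rescue surgery or stopping for worsening without documented progression.

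- All counted: S(t) = exp(−h·t), median = ln 2 / h.
- Share *f* censored: the Kaplan-Meier curve estimates exp(−(1−f)·h·t), median = ln 2 / ((1−f)·h).
- Ratio of medians = 1/(1−f).

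For a 12-month figure, take an assumed median of 24 months when all events count, so h = ln 2/24. Then S(12) = exp(−ln 2 × 12/24) = 0.707, and with a share censored S(12) = exp(−(1−f) × ln 2 × 12/24).

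| f | Median ratio | S(12) with share censored | Excess over 0.707 |
|---|---|---|---|
| 10% | 1/0.90 = 1.11 | 0.732 | 2.5 points |
| 20% | 1/0.80 = 1.25 | 0.758 | 5.1 points |
| 30% | 1/0.70 = 1.43 | 0.785 | 7.8 points |
| 40% | 1/0.60 = 1.67 | 0.812 | 10.5 points |

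A small simulation checked that this survives small numbers. It used 10, 15, 20 or 25 responders, 1,500 runs per setting, affected patients censored at the last of six-monthly scans, and administrative censoring between 6 and 36 months. The average 12-month estimate was 0.729 to 0.734 at f = 10% and 0.804 to 0.814 at f = 40%. It was 0.702 to 0.715 when all events counted.

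**The case against.** The strongest reply is that DOR to progression or death is the protocol's own endpoint, stated consistently in its objectives, endpoints and analysis sections. The surgery and discontinuation criteria belong to a binary endpoint at a fixed time, and the SAP's DOR set already excludes patients who failed by them. Adding clinical events is then a choice of estimand. This stands: a reader might infer that the SAP contradicts itself and must make rescue surgery a DOR event, but the documents do not require that. Protocol 6.11 also relies on independent radiologists to limit investigator bias, and a retrospective judgement that surgery was a rescue would bring some of that bias back.

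Two further inferences go too far:

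- **That progression after stopping or surgery is rarely captured.** Rescue surgery and progression overlap by definition, all available scans go to the central vendor, and data run to 30 days after the last dose. Worsening that is imaged is captured. The documents support only that some may be missed.
- **That debulking lowers the next volume and so keeps the patient in response.** How operated lesions are measured would be a matter for the Independent Central Review Charter, which is not among the documents. Masking is a possibility, not a stated effect.

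The impact is also limited. DOR is secondary, descriptive and listed by patient, and its median is shown only if there are enough responses. Surgeries and discontinuation reasons are tabulated under objective #5, though not linked to responders.

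The omission itself remains: the handling of these patients is unstated, and no DOR analysis tests it.

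**Conclusion.** The point holds as a gap in specification. A responder with later rescue surgery, or who stops alpelisib for worsening, is not a DOR failure unless a scan documents progression. Where no such scan exists, censoring is informative and DOR can be overstated.

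The size is unknown. With an assumed 10% to 40% of response-ending events affected and constant hazards, the median is inflated by about 11% to 67%. With an assumed 24-month median, the 12-month event-free proportion is about 2.5 to 10.5 percentage points too high. Both are measured against an analysis that counts these events. If worsening is nearly always imaged first, the effect is close to nil.

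A reader might build a larger effect from a few invented patients, for example 12 responders with 2 counted and 3 uncounted failures: 10/12 = 83% against 7/12 = 58% event-free. That is a single scenario that ignores other censoring and assumes 3 of 5 failures (60%) are missed. The documents do not support it as an estimate.

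The primary endpoint is unaffected. The change is worth making because DOR will be read as evidence of lasting benefit.

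**What to change.** 1. Keep the protocol's DOR definition as the main analysis. State in SAP 3.6 that a responder with rescue surgery or permanent discontinuation, and no documented progression, is censored at the last adequate scan before that event.
2. Add a supplementary Kaplan-Meier DOR analysis with two further events: rescue surgery for disease deterioration, at the surgery date, and permanent discontinuation for disease progression or lack of efficacy.
3. Report how many responders were censored in the main analysis for each of these reasons.

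This concerns endpoint coding only and changes no clinical rule. It needs a few SAP sentences and one extra output, because surgeries and discontinuation reasons are already planned for collection.

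The costs are real but small. The supplementary DOR may be shorter. Partial surgery dates are imputed under SAP Table 4-3: in a year after the index year, a date with only the year known becomes 1 January. Some event times will therefore be rough, and an imputed date could fall before the response, so such cases should be flagged. Discontinuation reasons are reported only where available, so some stops for worsening may still go uncounted.

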#### **Patient journey**

- Physician narratives (i.e. a generated summary describing the patient's clinical history of PROS, comorbidities, treatment history [medications, surgeries and medical interventions such as sclerotherapy and endovascular occlusive procedures] and mobility), and discussion on selected target lesions and how their changes correlate with change in function/symptoms and timing of response.
- Imaging scans, photographs and/or videos, where available with at least one corresponding baseline image/video.

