3.6 Secondary endpoints

Secondary endpoints will be used to support the efficacy of alpelisib, to provide a more complete description of the impact of alpelisib on the heterogeneous manifestations of PROS and to evaluate the safety and tolerability of alpelisib.

All the secondary endpoints including the safety analysis will be reported using the full population, to analyze data over time all available data will be used (Section 3.6.2). No imputation methods will be performed.

Endpoint #1: Percent change in the sum of target lesion (1 to 3 lesions) volume, as assessed by a central review of imaging scans, as measured by the change between the index date (or up to 24 weeks prior) and key time-points following the index date.

Endpoint #2: Percent change in sum of all measurable lesions (target and non-target) volume, as assessed by a central review of imaging scans, as measured by the change between the index date (or up to 24 weeks prior) and key time-points following the index date.

Endpoint #3: Percent change in the sum of all measurable non-target lesion volume, as assessed by a central review of imaging scans, as measured by the change between the index date (or up to 24 weeks prior) and key time-points following the index date.

In order to comprehensively demonstrate the efficacy of alpelisib treatment on target lesions, the percent change will be evaluated and reported at predefined time points throughout the study period (Section 3.3), under the assumption that a considerable number of patients have been treated for longer than 24 weeks.

Similarly as endpoint #1, the change in all measurable lesions, including the non-target, need to be assessed to confirm the potential benefit of alpelisib.

The percent change in the sum of measurable lesion volume (target and non-target) for each patient from index date to a generic key time point X (with X = 4, 12, 24, 36, 52 etc), will be calculated using the following equation:

$$\frac{\text{Sum}(\text{volume1}_{X\text{weeks}}, \text{volume2}_{X\text{weeks}}, \text{volume3}_{X\text{weeks}}) - \text{Sum}(\text{volume1}_{\text{index}}, \text{volume2}_{\text{index}}, \text{volume3}_{\text{index}})}{\text{Sum}(\text{volume1}_{\text{index}}, \text{volume2}_{\text{index}}, \text{volume3}_{\text{index}})} \times 100\%$$

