Proportion of patients receiving non-drug treatment	Binary	Frequency, percentage,	Overall during study period ;
Reasons for discontinuation of non-drug treatment (e.g., lack of efficacy, preparation for medical procedure)	Categorical	Frequency, percentage	Overall during study period;
Proportion of patients with surgery	Binary	Frequency, percentage	Overall during study period
Proportion of patients with surgery by type (e.g., amputation, debulking, scoliosis, epiphysiodesis)	Categorical	Frequency, percentage	Overall during study period
Number of surgeries	Continuous	N, mean, median, standard deviation, Q1, Q3, minimum and maximum	Overall during study period

Endpoints related to secondary objective #6: Change in PROS symptoms and complications

The following endpoints are included to establish an association between the efficacy of alpelisib (as measured by the primary endpoint) and any improvement seen on the symptoms and complications experienced by the patient.

PROS symptoms and complications between the index date and key time-points following the index date ([Table 3-1](#)) will be reported.

Type of PROS symptoms and complications and comorbidities will be coded using the Medical Dictionary for Regulatory Activities (MedDRA) terminology. The MedDRA version used for reporting will be specified in the CSR and as a footnote in the applicable tables/listings. Summaries will be presented by primary system organ class (SOC) and preferred term (PT). Severity as defined by the investigator and directly abstracted in the CRF will also be summarized. Results may be also reported graphically.

Moreover, the same measure will be assessed, as available, for the pre-index period and reported separately, to describe the symptoms and complications experienced by the patient before starting alpelisib.

Results of a questionnaire recording pain severity (i.e. Wong Baker, FLACC and Numerical scale rating) will be summarized at the index date and the proportion of patients with “improvement”, “worsening” and “stable” will be reported at 12 weeks, 24 weeks or 6 months, 52 weeks and at the “End of study”, all other time points will be listed.

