Proportion of patients with improvement, worsening and stable in pain severity	Binary	Frequency, percentage	At key time-points
Pain reduction (indicator)	Binary	Frequency, percentage	At week 24 time-point

Endpoints related to secondary objective #7: Change in functional status

The following endpoints are included for analysis to describe any improvement in PROS patients being able to return to, or improve their attendance at work/school, as well as any change in their ability to undertake usual activities of daily living, such as improvements in mobility. It is anticipated that the data availability associated with these endpoints may not be consistent across all patients/sites; however it will be reported as available and utilized also to generate physician narratives.

The number of patients attending work/school/pre-school will be summarized at the index date and the percentage of patients reporting improvement, worsening or stable at each time-point will be reported. The reason for change of status will be listed where available.

Frequency counts and percentages will be presented for mobility assessments at the index date and at key time-points. Performance status scores (ECOG, Lansky, Karnofsky) will be reported appropriately by age category, at the index date and the percentage of patients reporting improvement, worsening or stable in score will be summarized at baseline, 12, 24 and 52 weeks windows as well as the "End of study".

For work attendance:

- "Improvement" is defined as a shift from reporting of "No attendance" to "Part-time" or "Full time", from "Part-time" to "Full-time", as well as from "Unemployed" to "Part-time" or "Full-time" work.
- "Worsening" is defined as a shift from reporting of "Part-time" to "No attendance", "Full-time" to "Part-time" or "No attendance" as well as "Part-time" or "Full-time" to "Unemployed" status.

Similarly, for school attendance:

- "Improvement" is defined as a shift from reporting of "No attendance" to "Part-time" as well as, "Part-time" or "No attendance" to "Full-time";
- "Worsening" is defined as a shift from reporting of "Part-time" to "No attendance", as well as from "Full-time" to "Part-time" or "No attendance".

Work attendance will only be reported for the adult patients (i.e., ≥ 18 years of age) while school attendance will be reported for both pediatric and adult patients

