3.6.1 Statistical methods for the secondary endpoints

The secondary analyses for this study will be descriptive in nature and therefore no hypothesis testing will be performed. Descriptive analyses will be conducted where continuous data will be summarized by measures that will include the N, mean, median, standard deviation, Q1, Q3, minimum and maximum. Categorical and binary data will be presented by frequency counts and percentages.

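### SAP 3.6 gives the objective #5 and #6 endpoints the purpose of establishing an association with lesion response, but every measure visible in Tables 3-4 and 3-5 is a one-way summary that cannot show one.

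*SAP*

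**What the plan says.** SAP 3.6 states a relational purpose twice.

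- **Objective #5:** data on PROS-related medication and non-drug treatment "will allow to establish an association between the efficacy of alpelisib (as measured by the primary end point) and symptomatic/clinical benefit".
- **Objective #6:** "The following endpoints are included to establish an association between the efficacy of alpelisib (as measured by the primary endpoint) and any improvement seen" in symptoms and complications.

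The analysis rules are these.

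- **Population (SAP 3.6):** "All the secondary endpoints including the safety analysis will be reported using the full population".
- **Method (SAP 3.6.1):** "The secondary analyses for this study will be descriptive in nature and therefore no hypothesis testing will be performed", and "Categorical and binary data will be presented by frequency counts and percentages".
- **Measures:** Table 3-4 (objective #5) and Table 3-5 (objective #6), as numbered in the body of the SAP, list counts and percentages or N, mean, median and so on, overall or at time points. A typical row is "Proportion of patients with improvement, worsening and stable in pain severity". The Week 24 pain-reduction indicator is likewise a single overall percentage.
- **Subgroups (SAP 3.5.4):** these apply to the primary endpoint only, and response status is not among them.

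Outside the tables, Protocol 6.3 (Patient journey) asks each physician narrative for a "discussion on selected target lesions and how their changes correlate with change in function/symptoms and timing of response".

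**The concern.** An association is a statement about the same patients: who responded and who also improved. Separate percentages for response and for improvement do not contain that information. The full population also includes patients who carry none of it, because they have no target lesion, no baseline scan or a missing Week 24 response.

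The link matters. Protocol 6.3.1 justifies the volume endpoint first as objective, quantitative and widely observable. It then adds that the endpoint is associated with clinical benefit, citing a published 19-patient compassionate-use series. Protocol section 4 and SAP 1.1 say those 19 patients are intended to be included in this study, so the citation is not independent support. Protocol 6.8.1 judges efficacy on the totality of primary and secondary evidence, and Protocol section 9 intends the results for health authorities. A reader would find response and improvement percentages under a stated purpose of association, with no visible table showing whether they belong to the same patients.

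**Working it through.** **1. The plan's own figure.** The only design figure is Protocol Table 6-2: two-sided 95% Clopper-Pearson limits at n = 50. For x events the lower limit is the 0.025 quantile of Beta(x, n-x+1), and the upper limit is the 0.975 quantile of Beta(x+1, n-x). With x = 10, 15, 20 and 25 the limits are 0.100-0.337, 0.179-0.446, 0.264-0.548 and 0.355-0.645. All match the table. The point does not depend on them; they supply n = 50 and a range of response rates.

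**2. Is any visible measure split by response?**

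| Place in SAP | What is conditioned on | Relates symptoms or medication to response? |
|---|---|---|
| 3.6, Table 3-4 (#5) | nothing; exposure also by age | no |
| 3.6, Table 3-5 (#6) | severity, impact, time point | no |
| 3.6, duration of response (#4) | responders only | no; contains no symptom or medication measure |
| 3.5.2, completeness of response | with or without a Week 24 assessment | no; compares demographic and clinical characteristics |
| 3.5.4, subgroups | age, sex, mutation, PROS subtype, lesion type | no; primary endpoint only |
| 3.6.1, methods | nothing | no correlation, stratified summary or model |

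**3. What one-way percentages allow.** The documents give no symptom rates, so the counts are assumptions. Take N = 50, R = 20 responders and I = 25 with pain reduction. Let *a* be the responders with pain reduction. It can range from max(0, R+I-N) = 0 to min(R, I) = 20. The difference is a/20 - (25-a)/30. With b = 25-a, c = 20-a and d = 30-b, phi = (ad - bc)/√(20·30·25·25).

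| a | Responders | Non-responders | Difference | phi |
|---|---|---|---|---|
| 0 | 0/20 | 25/30 | -0.83 | -0.82 |
| 5 | 5/20 | 20/30 | -0.42 | -0.41 |
| 10 | 10/20 | 15/30 | 0 | 0 |
| 15 | 15/20 | 10/30 | +0.42 | +0.41 |
| 20 | 20/20 | 5/30 | +0.83 | +0.82 |

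The planned outputs read 40% response and 50% pain reduction in every row.

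**4. Range over the Table 6-2 response rates, keeping 25/50 improved.** For R of 25 or fewer, the extremes are 0 - 25/(50-R) and 1 - (25-R)/(50-R).

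- R = 10: 0 - 25/40 = -0.63 to 1 - 15/40 = +0.63.
- R = 15: 0 - 25/35 = -0.71 to 1 - 10/35 = +0.71.
- R = 20: -0.83 to +0.83.
- R = 25: -1 to +1.

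The sign is undetermined throughout.

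**5. What a cross-tabulation would deliver.** Newcombe 95% intervals for the difference, again with 25 of 50 improved and assumed splits:

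| Responders | Non-responders | Difference | 95% CI | Width |
|---|---|---|---|---|
| 15/20 | 10/30 | 0.42 | 0.13 to 0.61 | 0.48 |
| 10/20 | 15/30 | 0 | -0.26 to 0.26 | 0.52 |
| 15/25 | 10/25 | 0.20 | -0.07 to 0.44 | 0.51 |
| 10/15 | 15/35 | 0.24 | -0.06 to 0.47 | 0.53 |
| 7/10 | 18/40 | 0.25 | -0.09 to 0.49 | 0.58 |

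Fifty patients with both measures is optimistic, since 50 is the assumed number of participants before any loss to missing scans or pain data.

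**6. A complication.** SAP 3.5.1 also classes as non-responders patients who stopped alpelisib before 24 weeks, had rescue surgery or had an unmeasurable scan. SAP 1.3 ends data collection 30 days (30/7 = 4.3 weeks) after the last dose, and the Week 24 window opens at 20 weeks. A patient who stopped before about week 20 - 4.3 = 15.7 therefore has a response status but cannot have Week 24 symptom data.

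**The case against.** The strongest reply is that nothing formal is left unanswered. SAP 1.2 words objective #5 as assessing therapies over time and objective #6 as assessing changes in symptoms. The planned tables do that, and the association wording sits only in explanatory sentences. This stands, and it limits the point to two sentences and the output they lack. A reader might infer that a study objective cannot be met; the documents do not support that.

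A reader might also infer that no planned analysis anywhere addresses the link. That goes too far. Two headings after SAP 3.6.2 are redacted, as is the text there, and SAP 3.2 redacts a word describing further efficacy analyses. A relevant analysis may sit in that text. The objective #5 and #6 text and tables are readable, however, and contain none.

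Objective #7 (Table 3-6) should not be drawn in, because its endpoints are included to describe improvement and claim no association.

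The narratives do address the link patient by patient, which is defensible in so heterogeneous a disease. They are qualitative, and no visible SAP output aggregates them.

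That the study is descriptive does not answer the point, because a response-by-improvement table is descriptive and needs no test. Small numbers are a fair objection to the word *establish*. They do not justify leaving the table out.

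**Conclusion.** The mismatch holds for objectives #5 and #6 in the readable SAP: a stated analytic purpose has no summary that could serve it. Under the assumed margins (20 of 50 responders, 25 of 50 improved) the visible outputs are compatible with any difference from -83 to +83 points, and other response rates in Table 6-2 give limits from ±63 to ±100. The exact limits depend on the assumed counts. That the direction cannot be identified does not, as long as both responders and non-responders exist and some but not all patients improve.

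The consequence is modest. No stated figure is wrong and the primary result is untouched. The limit concerns the planned outputs: the patient-level data would allow the comparison. It would be speculation to infer that the report will claim an unsupported association, or that improvement in fact fell among non-responders.

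**What to change.** 1. In SAP 3.6, change *establish* to *describe* in the objective #5 and objective #6 introductions.
2. Add one descriptive table in efficacy-population patients with a non-missing Week 24 response. By responder and non-responder, show the Week 24 pain-reduction indicator, pain score improved/stable/worse, and receipt of PROS-related medication at index and at Week 24. Give counts, numbers missing and exact 95% CIs.
3. Within non-responders, show those who failed on volume criteria separately from those so classed because of discontinuation, rescue surgery or an unmeasurable scan. Add a plot of percent change in target-lesion volume by pain-change category among patients with paired volumes.

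The cost is two reworded sentences, one table and one figure, with no new data. The pain indicator and pain-score categories are already defined in SAP 3.6, and medication receipt at Week 24 is already reported in Table 3-4. Receipt at index should follow from medication start and stop dates. Categories such as symptom resolved/new or medication stopped/started are not visibly derived in the SAP, so they are not requested.

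The downside is small cells and intervals about 0.5 wide or more for a difference. The table should be labelled descriptive, with a note that without a control group it does not show that lesion shrinkage caused the benefit.
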